#### 13.1.1b Tumor Biopsy Only at Diagnosis (Stage III)

- PRETEXT 2 with *less than* 1 cm radiographic margin on the middle hepatic vein, the retrohepatic IVC, and the portal bifurcation.
- PRETEXT 3.
- PRETEXT 4.
- Biopsy technique at the discretion of the treating institution may be a percutaneous tru-cut, laparoscopic tru-cut or wedge, or open biopsy. Minimum biopsy size is 3 tru-cut cores of tissue. Larger biopsies, however, are strongly recommended where feasible to evaluate for the possibility of heterogenous foci of small-cell undifferentiated (SCU) tumor. (See [Section 14.0](#) for Pathology specimen requirements.)

#### 13.1.2 Tumors Considered Resectable After First 2 Cycles of C5VD Neoadjuvant Chemotherapy

##### Non-Extreme Resection

See [Section 14.0](#) for Pathology specimen requirements.

- Tumors with POST-TEXT 1.
- Tumor with POST-TEXT 2 with > 1 cm radiographic margin on the middle hepatic vein, the retrohepatic IVC, or the portal bifurcation.

#### 13.1.3 Tumors With Potential Need for Liver Transplant or Extreme Resection

- Definition of potential candidate for liver transplant or extreme resection based upon radiographic imaging obtained at diagnosis (PRETEXT) and after the SECOND cycle of C5VD chemotherapy (POST-TEXT):
  - Major Venous Invasion: Unifocal PRETEXT/POST-TEXT 3 with tumor ingrowth of all 3 hepatic veins or the retrohepatic vena cava (+V), or portal vein or both right and left (+P). The distinction between major venous “ingrowth” by tumor vs major venous “displacement” or “extrinsic compression” by tumor can be radiographically very difficult. Clinicians are encouraged to err on the side of “possible invasion” and refer patient for transplant evaluation if this distinction is very difficult to make.

- Unifocal PRETEXT/POST-TEXT 4
- Multifocal PRETEXT/POST-TEXT 3 and 4
- **Refer to surgical center with expertise in pediatric liver transplant and “extreme” liver resection at diagnosis if possible and no later than the first day of the 3rd cycle of C5VD neoadjuvant chemotherapy.** Resection planning is to be completed before completion of the 4th cycle of chemotherapy. Transplant or “extreme” resection is to occur within 4 weeks of completing the 4th cycle of chemotherapy.

#### 13.1.4 Tumors Considered Resectable Within 4 weeks of Completing 4th Cycle of Chemotherapy Non-Extreme Resection

See [Section 14.0](#) for Pathology specimen requirements.

- Tumors with POST-TEXT 3 and no major venous invasion. The surgeon must anticipate the ability to achieve a negative surgical margin on the right/left hepatic vein, retrohepatic IVC, or portal bifurcation. Margin may be less than 1 cm if the surgeon feels a complete resection will be feasible without transplant and patient has completed 4 cycles of C5VD chemotherapy.

#### 13.1.5 Tumors Presenting with Metastatic Disease (Stage IV)

See [Section 14.0](#) for Pathology specimen requirements.

- Complete 2 cycles of upfront experimental window chemotherapy.
- Repeat radiographic imaging after completing upfront window therapy
  - Resect (non-extreme) tumors POST-TEXT 1 or 2 with > 1 cm radiographic margin on the middle hepatic vein, retrohepatic IVC, and portal bifurcation
  - For all others, proceed with 2 cycles of C5VD
- Repeat radiographic imaging after completing first 2 cycles of C5VD
  - Resect (non-extreme) tumors downstaged to POST-TEXT Group 1, 2, or 3 tumors with > 1 cm radiographic margin on right/left hepatic vein, retrohepatic IVC, and portal bifurcation.
  - For patients potentially needing liver transplant/extreme resection (see definition in [Section 13.1.3](#)), refer to surgical center with expertise in pediatric liver transplant and “extreme” liver resection at diagnosis if possible and no later than the FIRST DAY of the 3rd cycle of C5VD chemotherapy. Resection planning is to be completed before completion of Cycle 7 in high risk responders and before completion of Cycle 6 in high risk non-responders. Transplant or “extreme” resection is to occur within 4 weeks of completing the 7th cycle of chemotherapy in high risk responders and the 6th cycle of chemotherapy in high-risk non-responders.
  - Repeat chest CT scan must demonstrate complete clearance of pulmonary metastatic disease within 1 week prior to liver transplant.
  - Those patients with persistent extrahepatic disease, may be resected (not transplanted) at the discretion of the surgical center with expertise in pediatric liver transplant and “extreme” liver resection.
  - Those patients with persistent extrahepatic disease who are not anatomically resectable without transplantation will continue chemotherapy.

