#### 4.6 Treatment for High-Risk Patients (Stratum 4) - Regimen H

All high-risk patients will receive 2 cycles of vinCRiStine, irinotecan and temsirolimus (VIT), using a 5 day irinotecan schedule, as “up-front” window therapy on Regimen H. Each cycle lasts 21 days and cycles will start on Weeks 1 and 4. Antibiotics will be given to patients receiving irinotecan who develop chemotherapy-related diarrhea. See “Diarrhea Secondary to Irinotecan” in the Supportive Care Guidelines at: <https://members.childrensoncologygroup.org/prot/reference materials.asp> under Standard Sections for Protocols.

Following 2 cycles of VIT, patients will be evaluated for response (see [Section 10.3](#)). The assessment of response is based on central review of imaging, the alphafetoprotein values and sampling dates. The results of the central review will be returned to the institutional investigator within 3 weeks of submission of the imaging and AFP material. If there is a discrepancy between the assessment by central review and by institutional assessment, the study PI will discuss with the treating physician to resolve the discrepancy. If the investigator selects a post-induction regimen that is *not* indicated by the central review of response, the patient will be considered off protocol therapy as of the start date of consolidation therapy.

Patients who *respond* (demonstrate a complete or partial response) to VIT will then receive a total of 6 cycles of C5VD therapy and 2 more cycles of VIT. Following first 2 cycles of VIT, no further VIT should be given until after surgical resection/liver transplant to avoid potential surgical complications of thrombosis and wound dehiscence. Each cycle lasts 21 days. A total of 10 cycles of chemotherapy (6 cycles of C5VD and 4 cycles of VIT, including the “up-front” window therapy) will be given. VIT is intended to be given during Cycles 7 and 10. However, the order of chemotherapy cycles can be switched at the discretion of the treating oncologists and surgeons to optimize surgical outcomes and minimize complications.

Patients who *do not respond* to VIT will continue with 6 cycles of C5VD repeated every 21 days and receive no further VIT. A total of 8 cycles of chemotherapy (6 cycles of C5VD and 2 cycles of VIT, including the “up-front” window therapy) will be given.

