Tumors that are unresectable at diagnosis, even if metastatic disease is present, should be referred to a surgical center with expertise in pediatric liver transplant and “extreme” liver resection should be done as soon as possible. Optimally for planning purposes, this liver transplant consultation should be obtained at diagnosis and no later than the FIRST DAY of the 3rd cycle of C5VD chemotherapy. The consent for the PLUTO registry should be obtained within one month of liver transplant and usually is obtained by the liver transplant team.

For the purposes of this study, consultation will be defined and may be accomplished in one of two ways:

- The FIRST TIME there is documented telephone or email/letter contact and a request for consultation between the treating oncologist and the liver specialty/transplant team.
- The FIRST TIME radiographic films and referral material are sent to the transplant physician/team at the same or another institution and are formally reviewed by the transplant physician/team.

The liver specialty/transplant physician/team will communicate the result of this consultation back to the referring physician.

Resection planning is to be completed before completion of the 4th cycle of C5VD chemotherapy. See Surgical Guidelines in [Section 13.0](#).

Patients will be evaluated after every 2 cycles of C5VD chemotherapy that occur prior to resection. Patients may have their primary tumor removed whenever it is feasible. It is the intent of the treatment that patients should have their tumors removed surgically or by OLT at the latest after Cycle 6 in both responders and

non-responders (ie, after the 4th cycle of C5VD) so that they can receive post-operative cycles of chemotherapy.

Chemotherapy should resume as soon as possible after surgical resection. In most circumstances this can typically be achieved within 3 weeks following surgery. **Patients who do not resume post resection chemotherapy within 42 days of resection will be considered off protocol therapy but not off study.** Further treatment will be at the discretion of the treating physician. Patients will continue to be followed on the AHEP0731 off protocol therapy follow-up CRF.

Regardless of the timing of surgery, patients should receive the total number of cycles as described above.

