**Patients whose tumors remain unresectable at the completion of planned therapy will be considered to have experienced an adverse EFS event. No further protocol therapy is planned for such patients. These patients can be treated at the discretion of the primary physician.**

Patients with pulmonary metastases will receive the first 2 cycles of Regimen H chemotherapy described above. If metastases disappear with chemotherapy, no pulmonary surgical intervention will be performed. If metastases are persistent after 4 total cycles of C5VD chemotherapy and the patient is considered a candidate for liver transplant at that time, metastases are to be resected to render the patient free of extrahepatic disease prior to transplant. Transplant may then be undertaken. If the liver tumor can be primarily resected after either 2 or 4 cycles of C5VD chemotherapy without transplant, this should be performed and the final cycles of chemotherapy should be administered. If the metastases are still present, they should then be resected. Pulmonary metastectomy may be performed earlier in the course of therapy if it can be done without resulting in delays in the administration of scheduled chemotherapy.

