### 13.3 **Surgical Management of Pulmonary Metastasis**

Patients presenting with pulmonary metastatic disease (Stage IV) will receive the “up-front” window chemotherapy described above for high-risk patients. If metastases disappear with chemotherapy, no pulmonary surgical intervention will be performed. If metastases are persistent after 4 total cycles of C5VD chemotherapy and the patient is considered a candidate for liver transplant at that time, metastases are to be resected to render the patient free of extrahepatic disease prior to transplant. Transplant may then be undertaken.

If the liver tumor can be primarily resected after either Cycles 4 or 7 in high risk responders and after Cycles 4 or 6 in high-risk non-responders without transplant, this should be performed and the final cycles of chemotherapy should be administered. If the metastases are still present, they should then be resected. Pulmonary metastectomy may be performed earlier in the course of therapy if it can be done without resulting in delays in the administration of scheduled chemotherapy.

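### For Regimen H responders, Section 13 ties resection planning and surgery to Cycle 7, a VIT cycle, while Section 4.6 places both by Cycle 6 and before any further VIT

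*Combined protocol and SAP*

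**What the plan says.** Section 13.1.5 covers Stage IV tumors that may need transplant or extreme resection. It states: "Resection planning is to be completed before completion of Cycle 7 in high risk responders". The operation itself is then due no later than four weeks after Cycle 7 ends. For non-responders the same sentences name Cycle 6. Section 13.3 adds, for primary resection without transplant: "If the liver tumor can be primarily resected after either Cycles 4 or 7 in high risk responders".

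Section 4.6 describes the same patients differently.

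- On the cycle order: "VIT is intended to be given during Cycles 7 and 10".
- On VIT after the two window cycles: "no further VIT should be given until after surgical resection/liver transplant to avoid potential surgical complications of thrombosis and wound dehiscence".
- On planning: "Resection planning is to be completed before completion of the 4 th cycle of C5VD chemotherapy".
- On surgery: "It is the intent of the treatment that patients should have their tumors removed surgically or by OLT at the latest after Cycle 6". This is stated for responders and non-responders alike.
- On primary resection in patients with lung metastases, in a sentence otherwise parallel to the one in Section 13.3: "If the liver tumor can be primarily resected after either 2 or 4 cycles of C5VD chemotherapy without transplant".
- On flexibility: "the order of chemotherapy cycles can be switched at the discretion of the treating oncologists and surgeons to optimize surgical outcomes and minimize complications".

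Section 2.5 gives the reason for that flexibility: ideally, six weeks without temsirolimus before definitive resection. Immediately after its planning deadline, Section 4.6 sends the reader to Section 13.0, where the other deadline stands.

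**The concern.** The two sections differ on the exposure that the protocol itself tries to keep away from major liver surgery. A surgical team working from Section 13 could schedule an operation after a temsirolimus cycle. An oncologist working from Section 4.6 would schedule it before that cycle. Nothing in the text says which deadline governs, and the pointer from Section 4.6 to Section 13.0 leads from one to the other.

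The stake is perioperative safety and consistent delivery of treatment in responders. The primary response assessment in Stratum 4 is made after Cycle 2, before the disputed point, and is not affected.

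**Working it through.** **Cycle count.** Sections 4.1 and 4.6 give the planned sequences in 21-day cycles.

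- Responders: VIT, VIT, C5VD ×4, VIT, C5VD ×2, VIT. The second C5VD cycle is Cycle 4, the fourth is Cycle 6, and Cycle 7 is VIT.
- Non-responders: VIT ×2, C5VD ×6. The fourth C5VD cycle is again Cycle 6.

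This reproduces Section 4.6's own statement that the fourth C5VD cycle is Cycle 6 in both groups.

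**Responder timings side by side.**

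| Item | Section 4.6 | Section 13 |
|---|---|---|
| Planning complete | before the end of the fourth C5VD cycle (Cycle 6) | before the end of Cycle 7 (13.1.5) |
| Latest surgery | after Cycle 6 (intent) | up to 4 weeks after Cycle 7, transplant or extreme resection (13.1.5) |
| Primary resection without transplant | after 2 or 4 C5VD cycles (Cycles 4 or 6) | after Cycles 4 or 7 (13.3) |
| Further VIT | after surgery | Cycle 7 VIT comes first in the planned order |

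The imaging schedule follows Cycle 6. Section 7.5 (footnote 5) and Section 15.3 (footnote 4) place responder tumor evaluations after Cycles 2, 4, 6 and 10, with none after Cycle 7. Section 13.1.5 adds only a chest CT shortly before transplant.

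**Does switching the cycle order help?** There are two cases.

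- If VIT waits until after surgery, Cycles 3 to 7 are all C5VD. Surgery after Cycle 7 then follows a fifth C5VD cycle, past the point in Section 4.6.
- If Cycle 7 is the fourth C5VD cycle, one of Cycles 3 to 6 must be VIT. VIT then precedes surgery, against Section 4.6.

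No order makes surgery after Cycle 7 agree with both parts of Section 4.6.

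**Days from last temsirolimus dose to surgery** (planned order, no delays, doses on Days 1 and 8 per Section 4.6.4).

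- Section 13: the last dose is Cycle 7 Day 8, study day 6×21 + 8 = 134. Cycle 7 ends on day 7×21 = 147. The gap is 147 − 134 = 13 days, rising to 13 + 28 = 41. If completion means the next Day 1, it is 14 to 42.
- Section 4.6: the last dose is Cycle 2 Day 8, study day 21 + 8 = 29. Cycle 6 ends on day 6×21 = 126. The gap is 126 − 29 = 97 days, or 98 on the other count.
- Against six weeks (42 days): of the 29 possible surgery days (0 to 28 after Cycle 7), all 29 fall short on the first count and 28 on the second. The one-week surgical tolerance in Section 4.0 could extend the latest gap to 48 or 49 days.

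**How many patients.** Section 9.2 plans 41 evaluable and 43 enrolled patients, with design response rates of 45% and 65%.

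- All responders (an upper bound): 41 × 0.45 = 18.5 and 41 × 0.65 = 26.7; 43 × 0.45 = 19.4 and 43 × 0.65 = 28.0.
- Illustration for the transplant or extreme-resection sentence: in INT-0098, 2 + 8 = 10 Stage IV patients had potentially unresectable tumors (Section 9.2), out of 40 Stage IV patients (Section 2.3.3), or 25%. PRETEXT grouping was possible for 155 of 182 patients. If that held equally across stages, the denominator is 40 × 155/182 = 34, giving 29%. Then 41 × 0.45 × 0.25 = 4.6 and 43 × 0.65 × 0.29 ≈ 8, so about 5 to 8 responders.

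**The case against.** The strongest reply is that the protocol already keeps VIT away from surgery in several places. Besides the text of Section 4.6, the responder delivery maps for Cycles 3–6, Cycle 7 and Cycle 10 (4.6.10.a, b and d) all say surgery should come before further VIT. Operating after a Cycle 7 temsirolimus dose would mean disregarding them. The deadlines are also partly nested, since planning finished by Cycle 6 also meets the Cycle 7 limit. The Section 4.6 timing is worded as an intent or ideal, and cycle order may be changed. Section 13 does not put all surgery at Cycle 7: simpler resections may come after the window or after two C5VD cycles. Finally, the front matter gives study closure as July 20, 2018, before this version of 11/07/18, so few patients may still reach the disputed point.

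Much of this stands as to likelihood and number. It does not remove the conflict. Read as an outer limit, Section 13.1.5 still sets a different limit from Section 4.6, and in the planned order that later limit follows a VIT cycle. Switching cycles does not help, as shown above. The maps sit in the treatment section, whereas the surgical instructions are in Section 13.

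The day comparison can fairly be called uneven, because four weeks are added on one side only. Adding them to both gives 13 to 41 days against 97 to 125, and the conclusion is unchanged. The patient counts deserve caution. The first is an upper bound. The second carries an at-diagnosis share over to responders and does not estimate how many would reach Cycle 7 unresected. Section 2.5 also reports 38 rather than 40 metastatic patients in INT-0098, but 10/38 = 26% lies within the range used.

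**Conclusion.** The contradiction is real and lies in current text. For Regimen H responders, Sections 13.1.5 and 13.3 give a planning deadline, a transplant or extreme-resection window and one primary-resection option tied to Cycle 7. Section 4.6 ties the same steps to Cycle 6 and to a period free of further VIT. In the planned order this is the difference between roughly 2 to 6 weeks and about 14 weeks since the last temsirolimus dose, assuming 21-day cycles without delay. It concerns a surgical hazard the protocol names, so the text must be reconciled.

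The number affected is unknown: fewer than the 18 to 28 responders expected under the design, with 5 to 8 only as an illustration under the assumptions stated.

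The Cycle 7 wording may be left over from Regimen W. With one VI cycle between two-cycle C5VD blocks (Section 4.1), the fourth C5VD cycle was Cycle 7. That is an inference; the document does not say so.

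**What to change.** Reconcile Sections 13.1.5 and 13.3 with Section 2.5, Section 4.6 and its responder maps (4.6.10.a, b and d). One statement in Regimen H cycle numbers should fix planning and surgery relative to VIT. Check it against Section 13.1.3, to which 13.1.5 refers and which counts to the fourth cycle of chemotherapy, and align it with the imaging schedule in Sections 7.5 and 15.3. The study team decides which timing applies.

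A separate, minor point that carries no weight here: the non-responder map for Cycles 3–6 (4.6.11.a) points to 4.6.10.b, the responders' VIT map, to start Cycle 7, although non-responders receive no further VIT. Section 4.6.9 names 4.6.11.a and 4.6.11.b for them, so the reference should be reconciled with that text.

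The cost is a wording amendment and one cross-reference, with no new procedures or patients.

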### 13.1.6 Optional Central Assistance to Aid in Determination of Tumor Resectability

If the treating physicians/surgeons desire assistance with their clinical decision making this will be available from one of the study surgeons on the Surgical Review Committee with expertise in the treatment of pediatric liver tumors. Clinical consultation is NOT REQUIRED. However, at least one of these surgeons will be available AT ALL TIMES for emergent consultation. The local treating institution is ultimately responsible for making the treatment decision regarding resectability with the full backup of the OPTIONAL consultation. The consulting surgeon on call can be reached by contacting the surgical study chair or the study chair.

### 13.2 **Central Surgical Review**

For purposes of evaluating clinical predictive value and reproducibility of the PRETEXT system, central review will be completed for all scans obtained at diagnosis (PRETEXT) and after neoadjuvant chemotherapy (POST-TEXT). The central surgical review will be performed on an ongoing basis by the team of study surgeons by web access to imaging coordinated through IROC RI (QARC) and completed by the team of surgeons and radiologists. A bi-annual group review of imaging will be held to achieve consensus on imaging where central review is divergent amongst the reviewers

### 13.3 **Surgical Management of Pulmonary Metastasis**

Patients presenting with pulmonary metastatic disease (Stage IV) will receive the “up-front” window chemotherapy described above for high-risk patients. If metastases disappear with chemotherapy, no pulmonary surgical intervention will be performed. If metastases are persistent after 4 total cycles of C5VD chemotherapy and the patient is considered a candidate for liver transplant at that time, metastases are to be resected to render the patient free of extrahepatic disease prior to transplant. Transplant may then be undertaken.

If the liver tumor can be primarily resected after either Cycles 4 or 7 in high risk responders and after Cycles 4 or 6 in high-risk non-responders without transplant, this should be performed and the final cycles of chemotherapy should be administered. If the metastases are still present, they should then be resected. Pulmonary metastectomy may be performed earlier in the course of therapy if it can be done without resulting in delays in the administration of scheduled chemotherapy.

### 13.4 **Liver Transplant or Extreme Liver Resection**

Two distinct cohorts of unresectable patients are expected. Patients identified as potentially unresectable based on preoperative radiographic imaging that are either: 1) successfully referred for evaluation at a transplant center in a timely fashion, or 2) not successfully referred for evaluation at a transplant center in a timely fashion. Within the first cohort there are further possible subgroups: 1a) prove to be resectable at the time of surgery; 1b) remain unresectable and primary transplant performed, 1c) remain unresectable, no surgery performed due to persistent metastatic disease unresponsive to chemotherapy or surgical resection, or 1d) do not proceed to surgery because of refusal or deteriorating patient condition.

Post surgery/transplant chemotherapy will be based on the chemotherapy received preoperatively. For patients with disease confined to the liver, 2 additional post operative/transplant cycles of the same chemotherapy given preoperatively (4 cycles) will be given postoperatively for a total of 6 cycles. For patients with metastatic disease, additional cycles of the same chemotherapy given pre-operatively will be given post-operatively. The number of post operative cycles may vary depending upon the point in treatment during which resection occurred for a total of 8 cycles for patients who did not respond to window therapy and a total of 10 cycles for patients who did respond to window therapy.

Patient management guidelines will follow the same format that has been discussed and agreed upon by an international committee of liver transplant surgeons in the preparation of the Pediatric Liver Unresectable Tumor Observatory (PLUTO). All patients treated by liver transplantation will be asked to sign a consent within one month (optimally) post transplant giving permission for registration on the PLUTO multi-center international cooperative database for children who receive a liver transplant for hepatoblastoma or hepatocellular carcinoma. The consent is usually obtained by the liver transplant team, but may also be obtained by the oncology team. Medical information is entered via a secure internet connection with a remote data entry system accessible at [www.pluto.cineca.org](http://www.pluto.cineca.org). The organization called CINECA is an information management organization with a contract with SIOPEL (the liver tumor study group of the Societe International Oncologie Pediatric (SIOP)) to collect and manage the information. Other children's liver study groups that participate in the registry include the Children's Oncology Group (COG), the German Pediatric Oncology Group (GPOH), the Study Pediatric Liver International Transplant group (SPLIT), and several independent liver transplant centers throughout the USA, Europe, South America, and Japan.

The database collects information about type of liver tumor, tumor size, number and location of tumors in and outside of the liver, involvement of blood vessels, chemotherapy medications used, lymphocyte blood count, immunosuppression medications used after transplant, side effects of the medications, at what point in the treatment was the transplant performed, complications from the transplant surgery, and outcome of the transplant and the disease free survival. The registry plans to enroll patients for a minimum of ten years with an enrollment of approximately 300. The registry currently plans to keep the entered data indefinitely. If subjects do not want to continue participating in the database, their data will be removed upon request. This database can be accessed via the PLUTO Registry Website: <http://pluto.cineca.org/access.htm>. In order to be authorized to use the transplant database, it is necessary to register with PLUTO. The link to the required participation form is found using the same PLUTO access link provided above.

The registry on the internet has a home page with basic information about what it is and about the organizations that have cooperated to make the registry possible. Access to the main part of the registry where the patient information is collected and stored is strictly controlled and requires a secure password which is available only to the research doctors approved by the registry. The registry is maintained by CINECA ([www.cineca.it](http://www.cineca.it)), a nonprofit consortium made up of 32 Italian Universities, the Italian National Institute of Oceanography and Experimental Geophysics, the Italian National Research Council, and the Italian Ministry of University and Research. CINECA supports the research activities of the scientific community through supercomputing and its applications. By contract with SIOPEL (International Childhood Liver Tumour Strategy Group), CINECA serves as the data management group for all SIOPEL studies. The PLUTO registry data are available to scientists/clinicians whose centers regularly contribute to PLUTO. Data can be used to perform scientific studies which have been approved by the PLUTO steering committee. To obtain access to data, a written request is addressed to the chairperson of PLUTO steering committee serving as custodian of the registry. The request must contain title, objectives and description of study, supporting letter of program director, name and affiliation of investigator, and a disclosure statement disclosing any potential conflicts of interest.

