### 4.1 Overview of Treatment Plan

AHEP0731 builds on the results of the last 20 years of hepatoblastoma clinical trials and seeks to diminish toxicity in the approximately 30% of low-risk patients, increase survival in intermediate-risk patients and identify new agents(s) that may be used in high-risk and recurrent patients.

All patients with Stage I PFH hepatoblastoma will be classified as very low-risk (Stratum 1) and will be treated with surgery only. Patients with Stage I non-PFH, non-SCU hepatoblastoma or with Stage II non-SCU hepatoblastoma will be classified as low-risk (stratum 2) and will be treated on Regimen T with 2 adjuvant cycles of cisplatin, 5-fluorouracil, and vincristine (C5V), a reduction from the standard 4 cycles of chemotherapy given on previous COG trials. Patients with Stage I SCU, Stage II SCU, or any Stage III hepatoblastoma will be classified as intermediate-risk (stratum 3) and will be treated with Regimen F (intermediate risk, stratum 3, has been closed to accrual as of 03/12/12). This treatment regimen is based on previous COG trials that administered 6 cycles of C5V therapy plus surgical resection of the tumor. However, to improve resection and survival rates, doxorubicin, an agent with proven efficacy will be added to the C5V therapy (C5VD). All patients with any Stage IV hepatoblastoma as well as patients with any stage of hepatoblastoma and initial AFP < 100 ng/mL will be classified as high-risk (stratum 4).

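### Section 13.4 sets post-surgery chemotherapy totals by disease extent instead of regimen, which contradicts 4.1 and 4.6 for non-metastatic Stratum 4 candidates for transplant or extreme resection

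*Combined protocol and SAP*

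**What the plan says.** The 13.4 paragraph on chemotherapy after surgery opens with a general principle: "Post surgery/transplant chemotherapy will be based on the chemotherapy received preoperatively". It then gives counts by disease extent.

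- Liver-confined disease: "For patients with disease confined to the liver, 2 additional post operative/transplant cycles of the same chemotherapy given preoperatively (4 cycles) will be given" after the operation, which the sentence adds up to 6.
- Metastatic disease: the number of postoperative cycles varies with when resection happened, "for a total of 8 cycles for patients who did not respond to window therapy and a total of 10 cycles" for those who did respond.

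Neither sentence names a stratum or regimen, and the paragraph does not refer back to Section 4.

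Section 4 assigns treatment by stratum. Besides Stage IV, 4.1 says that "patients with any stage of hepatoblastoma and initial AFP < 100 ng/mL will be classified as high-risk (stratum 4"). Its table has separate any-stage rows for AFP below 100 ng/mL, with the same totals as the Stage IV rows. Section 4.6 gives non-responders "A total of 8 cycles of chemotherapy (6 cycles of C5VD and 2 cycles of VIT") and responders "A total of 10 cycles of chemotherapy (6 cycles of C5VD and 4 cycles of VIT"), and adds: "Regardless of the timing of surgery, patients should receive the total number of cycles as described above". On timing, it intends that patients "should have their tumors removed surgically or by OLT at the latest after Cycle 6 in both responders and" non-responders, that is, after the fourth C5VD cycle.

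The 6-cycle course is that of Stratum 3 (Regimen F) in 4.5. Section 2.3.3 excludes AFP below 100 ng/mL from that stratum, which closed to accrual on 12 March 2012.

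**The concern.** A surgical or transplant team is likely to look in 13.4 for what follows the operation. A Stage III patient with AFP below 100 ng/mL fits the liver-confined sentence by its wording, but is a Regimen H patient under Section 4. The plan therefore states two different totals for the same child. Once Stratum 3 had closed, a newly enrolled patient with unresected, non-metastatic disease could only be a low-AFP Stratum 4 patient, so the sentence as worded no longer suited any new patient.

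Where 13.4 errs, it errs toward too few postoperative cycles. Section 2.4 cites a 3-year EFS of 13% for low-AFP patients.

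**Working it through.** **1. The plan's own totals.** Regimen F (4.5): 4 + 2 = 6. Regimen H (4.1, 4.6): non-responder 2 VIT + 6 C5VD = 8; responder 4 VIT + 6 C5VD = 10. Cumulative vincristine in Table 3 gives an independent check. A VIT cycle has 2 vincristine doses and a C5VD cycle has 3, each 1.5 mg/m².

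- Non-responder: (2 × 2 + 6 × 3) × 1.5 = 33 mg/m²
- Responder: (4 × 2 + 6 × 3) × 1.5 = 39 mg/m²

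Table 3 states 33-39, so 8 and 10 are the intended Stratum 4 totals.

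**2. Is the 6 a whole-course count?** The 8 and 10 in the same 13.4 paragraph include VIT cycles. Reading the 6 as C5VD cycles only would make the paragraph count in two different ways.

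**3. Who is affected?** Section 13.4 concerns potentially unresectable patients considered for transplant or extreme resection. Stage IV is metastatic and correctly covered. Low-AFP Stage I and II tumors are already resected, and 3.2.8.6 bars high-risk enrollment within 6 weeks of major surgery, which largely excludes them. That leaves Stage III with AFP below 100 ng/mL and a potential need for transplant or extreme resection. The documents give no number for this group. Stage III with abdominal node involvement is neither strictly liver-confined nor metastatic, so 13.4 gives it no clear total.

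**4. Size of the gap.** For these candidates, 13.1.3 places surgery within 4 weeks of the fourth chemotherapy cycle. It counts the referral deadline in C5VD cycles. Read with 4.6, this means after 2 VIT + 4 C5VD, the end of Cycle 6. Section 4.6 also allows earlier removal when feasible.

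| Surgery after | Given by then | Window response | Still due under 4.6 | Added under 13.4 | Resulting total | Gap |
|---|---|---|---|---|---|---|
| Cycle 6 (planned) | 2 VIT + 4 C5VD = 6 | Non-responder | 8 − 6 = 2 | 2 | 6 + 2 = 8 | 8 − 8 = 0 |
| Cycle 6 (planned) | 6 | Responder | 10 − 6 = 4 | 2 | 6 + 2 = 8 | 10 − 8 = 2 |
| Cycle 4 (permitted) | 2 VIT + 2 C5VD = 4 | Non-responder | 8 − 4 = 4 | 2 | 4 + 2 = 6 | 8 − 6 = 2 |
| Cycle 4 (permitted) | 4 | Responder | 10 − 4 = 6 | 2 | 4 + 2 = 6 | 10 − 6 = 4 |

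**5. What the missing cycles are.** Each C5VD cycle carries cisplatin 100 mg/m² and doxorubicin 2 × 30 = 60 mg/m². For a responder at the planned point, suppose the two added cycles are both C5VD. Then all 6 C5VD cycles are given and only 2 VIT cycles are lost. If instead they follow the Regimen H order (VIT, then C5VD), 5 C5VD cycles are given: cisplatin 500 of 600 mg/m² and doxorubicin 300 of 360 mg/m². Off the planned course, surgery after Cycle 4 followed by two C5VD cycles gives 4 C5VD cycles: 400 of 600 and 240 of 360 mg/m².

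**The case against.** The best defense is that the sentence describes Regimen F by its content: one regimen, four cycles before surgery and two after. The totals of 8 and 10 are tied to window response, which only Stratum 4 has, and the opening line points to what was given preoperatively. Elsewhere the plan uses metastatic or Stage IV as shorthand for Stratum 4, as in aim 1.2.3 and Hypothesis 1.3 in 9.2. The treatment-failure definition in 9.2 also ties cycle counts to stage. Section 13 is surgical guidance, whereas Section 4 prescribes the drugs. Central review after Cycle 2 tells the site which regimen follows, and choosing another takes the patient off protocol therapy. Accrual closed on July 20, 2018, before this version of 11/07/18.

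All of this makes misapplication unlikely, and it limits the point. It does not remove the conflict. Nothing in 13.4 confines the sentence to Stratum 3 or defers to Section 4, and the opening line is followed at once by counts keyed to disease extent. Closure is not decisive either. From July 20 to November 7 is 110 days, about 16 weeks, and the responder course runs to week 30. A patient enrolled just before closure could have been near the planned surgery point. Whether there was one is not stated.

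A reader might infer from 6 against 8 or 10 that every non-metastatic Stratum 4 patient would be left 2 or 4 cycles short. The documents do not support that. Ordinary resections fall under 13.1 and 4.6, not 13.4. For transplant or extreme-resection candidates on the planned course, six cycles have already been given and 13.4 adds two.

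**Conclusion.** The inconsistency is real and minor. On the planned course, the wording of 13.4 matches 4.6 for window non-responders and falls 2 cycles short for responders. The larger gaps of 2 and 4 belong to surgery after Cycle 4, a permitted departure from that course.

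This rests on three assumptions: the planned surgery point is the one in 4.6, the two added cycles in 13.4 are applied literally, and at least one patient meets all the conditions in step 3. The last may be false.

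Two further inferences are not supported. The documents report no patient treated under the shorter rule, so nothing shows that anyone was undertreated. Nor does the wording touch the Stratum 4 response analysis, because that endpoint is determined by the end of the two VIT window cycles, whereas 13.4 concerns cycles after later surgery.

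**What to change.** In 13.4, make Stratum 3 (Regimen F) patients the subject of the 6-cycle sentence, in place of those with liver-confined disease. Make all Stratum 4 (Regimen H) patients, whether or not metastatic, the subject of the sentences giving 8 and 10. This also gives a clear total to Stage III patients with nodal involvement. The cost is a brief rewording, with no new procedures, data collection or analyses.
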